14.0 BIOSTATISTICS

14.1 Statistical Plan for Assessment

14.1.1 Implant Failure

The primary objective of this study is to assess for the reduction of implant failure associated with multi-beam IMRT, compared to our published historical implant failure rates associated with conventional radiation techniques. The primary endpoint is incidence of implant failure by the end of the study period (24 months post-IMRT for Group 1, and 30 months post-IMRT for Group 2).

Our published data and recent findings in the literature suggested that the implant failure rate (implants that are removed or replaced by another reconstruction) was 20% at 24 months post-IMRT for group 1 [20] and 30% at 30 months post-IMRT for group 2 [51]. Assuming that 1/3 of the patients we will enroll are going to be in group 1 and the remaining 2/3 will be in group 2, we set up the hypotheses that an implant failure rate of 26% or more is considered unacceptable while 16% or less is considered acceptable. Since the endpoint cannot be measured until 2 years after the treatment, we will utilize a one-stage design. We will test the hypothesis using a binomial test based on a cohort of 100 patients. We insist that at minimum 34 of them will be enrolled in group 1 and at minimum 66 will be in group 2, and we will combine them for the primary objective. We will claim that multi-beam IMRT significantly reduces the implant failure rate if no more than 20 patients have an implant failure after IMRT within 24 months of the treatment for patients in group 1 or within 30 months after IMRT in group 2. For this decision rule, we have a type I error (i.e., claiming multi-beam IMRT promising while it is not) rate less than 0.10 and a type II error (i.e., claiming multi-beam IMRT not promising while it actually is) rate less than 0.15.

Because there is no reason why local control or lung or other toxicities would be impacted secondary to treatment with multi-beam IMRT instead of conventional treatment, an early stopping rule in order to detect early recurrences was not deemed necessary.

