We expect to accrue 3-4 patients per month. Thus, the trial should be completed within 3 years. Efforts will be made to follow-up every patient for at least 24 months (Group 1) or 30 months (Group 2). Since patients may drop off (for reasons unrelated to toxicity) or be lost to follow-up, we will enroll a total of 130 patients. However, only the first 100 patients (subject to the restriction that at minimum 34 are in group 1 and at minimum 66 are in group 2) who have been followed for at least 24/36 months from IMRT will be analyzed towards the primary objective. Only patients who are irradiated to a tissue expander or permanent implant will be counted in the analysis of the primary objective (i.e. patients in the cardiac substudies who do not receive IMRT to the tissue expander or implant will not be included in the analysis of the primary objective).

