14.1.2 Capsular Contracture

For the secondary objectives, the incidence of moderate and severe capsular contracture will be examined using proportions of patients who developed Baker grade <II and \geq II capsular contracture, respectively, at 12 or 18 months and 24 or 30 months after IMRT was administered. Incidence of minor revisional surgeries by plastic surgeon will be evaluated by proportions too. Again, the rates (proportions) will be compared across the two groups.

To evaluate cosmesis, the Breast-Q[®] will be utilized in these assessments and will be presented descriptively, giving summary statistics for changes in the Breast-Q[®] scores over time.

Post-treatment MRI outcome is defined as a continuous variable. We will examine the correlation between the 12-month MRI and 12-month Baker score (<II vs \geq II in Group 1 and between the 18-month MRI and 18-month Baker's score in Group 2. The correlation will be assessed by Wilcoxon rank sum tests. We will also examine the sensitivity and specificity of MRI by using Baker score as the gold standard. All patients enrolled will be used for the analysis of secondary objectives if they provided eligible measurements. Analyses for secondary objectives will be done separately for the two groups.

14.1.3 $^{13}\text{N-NH}_3$ PET/CT Feasibility Endpoint

We will assess the feasibility of performing $^{13}\text{N-NH}_3$ PET studies in breast cancer patients undergoing IMRT within the RT simulation session. This involves delivering the dose on time (taking into account the short half life of $^{13}\text{N-NH}_3$), performing all scans successfully, and most importantly, having the patient tolerate all imaging sessions while in the treatment position.

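### The primary test stops at the first 100 fully followed patients: if losses are smaller than allowed for, completed outcomes are left out of the verdict, and the rule for who counts is not fully defined

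*Combined protocol and SAP*

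**What the plan says.** Section 14.1.1 sets a one-stage design in which "an implant failure rate of 26% or more is considered unacceptable while 16% or less is considered acceptable". The historical failure rate behind this "was 20% at 24 months post-IMRT for group 1 [20] and 30% at 30 months post-IMRT for group 2 [51"]. The analysis size is fixed: "We will test the hypothesis using a binomial test based on a cohort of 100 patients". Success is declared "if no more than 20 patients have an implant failure after IMRT" by 24 months (Group 1) or 30 months (Group 2). The section states a type I error "rate less than 0.10" and a type II error below 0.15.

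Because some patients may drop off or be lost, "we will enroll a total of 130 patients". The next sentence limits the primary analysis: "However, only the first 100 patients (subject to the restriction" of at least 34 in Group 1 and at least 66 in Group 2) with at least 24/36 months of follow-up. The endpoint elsewhere in the section is at 24/30 months. Only patients irradiated to an expander or implant count.

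Section 14.1.2 treats the secondary objectives differently: "All patients enrolled will be used for the analysis of secondary objectives if they provided eligible measurements".

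**The concern.** Three things are left open in the sentence that defines the primary analysis set.

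- **Surplus patients.** No rule covers the 101st and later evaluable patients. Section 14.1.1 promises efforts to follow every patient to 24 or 30 months, so these outcomes would be collected and then not used for the main question.
- **Order.** *First* could mean by enrolment, by IMRT date or by completion of follow-up. These can give different sets of 100.
- **Early failures.** Read literally, a patient whose implant failed at, say, 8 months and who then left follow-up does not meet the follow-up condition, although her endpoint is known. This can happen even when there is no surplus.

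The verdict rests on a single count, 20 against 21, so a small change in who is counted can change it.

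**Working it through.** **Inputs.** From Section 14.1.1: p0 = 0.26, p1 = 0.16, n = 100, cut-off 20, historical rates 20% and 30%, minimums 34 and 66, enrolment 130, accrual 3-4 per month. From Section 14.1.4: 10 controls without IMRT. The documents give no expected loss rate.

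**Possible surplus.** 130 − 100 = 30, used up if 30/130 = 23% are lost. If the 10 controls are within the 130, 120 − 100 = 20, used up if 20/120 = 17% are lost.

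**The plan's own rule.** Type I error = P(X ≤ c | n, p0) and power = P(X ≤ c | n, p1), exact binomial.

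- P(X ≤ 20 | 100, 0.26) = 0.103, just above the stated limit of 0.10.
- P(X ≤ 20 | 100, 0.16) = 0.888, so type II error is 0.112, within the stated 0.15.

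The excess over 0.10 comes from rounding the null, not from the cap. The 34/66 mix gives (34 × 0.20 + 66 × 0.30)/100 = 0.266, and P(X ≤ 20 | 100, 0.266) = 0.081. Summing two separate binomials (34 at 20%, 66 at 30%) gives 0.080.

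**All evaluable patients, null held at 26%.**

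| N | Cut-off | Type I | Power |
|---|---|---|---|
| 100 | 20 | 0.103 | 0.888 |
| 110 | 22 | 0.090 | 0.896 |
| 120 | 24 | 0.079 | 0.904 |
| 130 | 26 | 0.069 | 0.911 |

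The last row applies only if all 130 are irradiated and none is lost. At N = 101-104, 106-108, 112 and 117, no cut-off lowers both errors below those of 20/100.

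**All evaluable patients, null at the group mix.** Without the cap, the mix is no longer held at 34/66. Type I error is P(X1 + X2 ≤ c), with X1 ~ Bin(n1, 0.20) and X2 ~ Bin(n2, 0.30). Power is at 16% overall.

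- N = 120 at about 34:66 (41/79): the largest cut-off with type I ≤ 0.10 is 25, with type I 0.089 and power 0.938. Type I is slightly higher than the current 0.080; power rises from 0.888.
- N = 120 at 54/66: 24 has type I 0.097, and power is 0.904.
- N = 130 at 64/66: 26 has type I 0.105, so the cut-off must be 25, with power 1 − 0.1315 = 0.869.
- N = 130 at 34/96: 26 has type I only 0.033.

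A single cut-off per N is therefore not enough; it must follow the mix.

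**Who is left out.** If N patients are evaluable with K failures, a random 100 passes with hypergeometric probability Σ(x ≤ 20) C(K,x) C(N−K,100−x)/C(N,100).

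- N = 110: 64% with 22 failures, 35% with 23.
- N = 120: 99% with 21 failures, 60% with 24, 41% with 25, 5% with 28.

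Over all outcomes at N = 120, the verdict from a random 100 (≤20) differs from the all-patient verdict (≤24) about 13% of the time if the true rate is 20-21%, and about 6% at 16% or 26%.

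**The case against.** A fixed sample with over-enrolment is a valid, pre-specified choice, and planned power already exceeds the promised 0.85. The minimums of 34 and 66 add up to exactly 100, so the cap also holds the analysed mix at the one assumed for the null. The extra patients are a loss allowance: Section 9.2.1 makes some patients inevaluable and Section 13.0 adds withdrawals, so there may be no surplus. The flip probabilities are largest next to the cut-off, as with any sharp rule. All of this stands, and it limits the size of the point. It does not supply a rule for surplus patients, a definition of *first*, or a way to count an early failure.

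A reader might infer more, in three ways that the documents do not support.

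- *That outcomes from up to 130 irradiated patients are discarded.* Section 1.0 describes the 20 sub-study patients as a subset, and 10 of them receive no IMRT. If they are within the 130, the ceiling is 120; the documents do not say.
- *That the cap always makes both error rates worse.* It does not at several small surpluses, and under the mix-based null at 120 the largest allowed cut-off raises type I slightly while adding power.
- *That the 100 are picked once failures are known.* The text pre-specifies the first 100. If ordered by enrolment or IMRT date, no discretion remains. The wording leaves the order open; it does not show selection.

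**Conclusion.** The point holds as a moderate, inexpensive improvement. If losses are below the allowance, the main verdict omits completed outcomes that the trial has collected. With 120 evaluable patients, using them all gives either lower error on both sides (0.079 and 0.904 at a fixed 26% null) or, with the null at the planned mix, a power gain from 0.888 to about 0.94 at type I of about 0.09. The benefit shrinks with a smaller surplus or a mix tilted towards Group 1, and disappears if about 17-23% are lost. The undefined order and the handling of early failures need settling in any case; the documents give no basis for sizing the latter. These figures assume independent outcomes, the plan's historical rates and, for the flip risk, a random set of 100.

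**What to change.** In Section 14.1.1:

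1. Define the primary set as every irradiated patient who reaches the endpoint date (24 months in Group 1, 30 months in Group 2) or has an implant failure earlier. Reconcile 24/36 with 24/30 months.
2. Keep the 34/66 minimums. For each N from 100 up, and each group mix, pre-specify the largest cut-off with exact type I error ≤0.10 under the 20%/30% null, and state the resulting power.
3. Add a cumulative-incidence estimate at 24/30 months as a sensitivity analysis, so that patients with partial follow-up contribute.
4. If the fixed 100 is kept, at least define *first* by enrolment or IMRT date, count early failures, and say how surplus patients will be reported.

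Cost: SAP wording and a cut-off table. The primary read-out comes later, by up to 30/4 = 7.5 to 30/3 = 10 months for 30 patients (5 to 6.7 months for 20), although the secondary analyses already use all enrolled patients. The cut-off becomes a function of N and mix, which is less simple to explain than 20 out of 100.

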The time interval at which follow-up assessments will occur after the intervention (IMRT) will depend on the sequencing of the expander/implant exchange with radiation. Two groups of patients will be evaluated. Group 1 will consist of patients who receive IMRT to the permanent implant and are followed up at 12 ± 2 months and 24 ± 2 months after IMRT. Group 2 will include patients who receive IMRT to the temporary expander and are followed up at $12-18 \pm 2$ months and 30 ± 2 months after IMRT. This sequencing will be determined prior to study enrollment based on whether the patient received neoadjuvant or adjuvant chemotherapy (see Section 3.0 for further details).

Evaluation for implant failure may occur at any time interval between the completion of IMRT to the end of the study period (24 ± 2 months for Group 1 or 30 ± 2 months for Group 2, after IMRT). Capsular contracture and cosmesis will be assessed at baseline, 12 ± 2 months and 24 ± 2 months for Group 1 or $12-18 \pm 2$ months and 30 ± 2 months for Group 2, both following IMRT. The patient will be evaluated for capsular contracture by physical exam and an optional breast MRI, and for cosmesis by Breast-Q[®] questionnaires at these time points. A subset of 10 patients evaluated with cardiac PET scans for exploratory objective #1 will obtain these studies at the time of the RT simulation session and $12-18$ months (± 6 months) after the completion of IMRT. A separate subset of 20 patients to be evaluated for exploratory objectives #2 and #3 will complete the study questionnaires and undergo speckle tracking strain echocardiography, ultrasound of the brachial artery, CPET, and cardiac biomarker measurement at baseline and at the post-treatment intervals specified in Section 10.

Target accrual for this study is 130 patients, to be achieved in 3-4 years of accrual.

Schema

¹**Group 1:** Physical examination by MD, optional Breast MRI, Breast-Q[®] at baseline (after permanent implant exchange, physical exam and Breast-Q[®] may be done after the initiation of IMRT), 12 ± 2 months and 24 ± 2 months post-IMRT. Total length of the follow-up time will be 24 ± 2 months post-IMRT.

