²**Group 2:** Physical examination by MD, optional Breast MRI, Breast-Q[®] at baseline (after permanent implant exchange and after IMRT), 18 ± 2 months and 30 ± 2 months post-IMRT, as these patients will undergo exchange of the temporary expander for the permanent implant approximately 4-8 months following the completion of radiation (at the discretion of the treating plastic surgeon). Total length of the follow-up time will be 30 ± 2 months post-IMRT.

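### The rule defining the 100-patient primary analysis set asks for 24/36 months of follow-up, while the Group 2 endpoint, decision rule and visit schedule all stop at 30 months

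*Combined protocol and SAP*

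**What the plan says.** Section 14.1.1 defines the primary endpoint as implant failure by the end of the study period, "24 months post-IMRT for Group 1, and 30 months post-IMRT for Group 2". Success is claimed if at most 20 of 100 patients fail, counting Group 2 failures "within 30 months after IMRT in group 2". At least 34 of the 100 must be in Group 1 and at least 66 in Group 2.

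The final paragraphs of that section set the follow-up aim: "Efforts will be made to follow-up every patient for at least 24 months (Group 1) or 30 months (Group 2"). They raise enrolment to 130 with the reason "Since patients may drop off (for reasons unrelated to toxicity) or be lost to follow-up". They then restrict the analysis to the first 100 patients "who have been followed for at least 24/36 months from IMRT will be analyzed towards the primary objective".

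The Group 2 note to the schema in Section 1.0 states "Total length of the follow-up time will be 30 ± 2 months post-IMRT". Sections 10.2 and 12.0 place the last Group 2 evaluation at 30 ± 2 months. Footnote c of the Group 2/2A schedule lets the plastic surgeon time follow-up visits from exchange surgery instead, and exchange takes place "approximately 4-8 months following the completion of radiation".

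**The concern.** The sentence containing 24/36 is the only one that says which patients enter the trial's single efficacy test. For Group 2 it requires six months more follow-up than the endpoint needs and more than the IMRT-timed schedule provides. Group 2 must supply at least 66 of the 100 patients.

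Three matters of membership are also left open:

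- whether a final visit inside the allowed window but before the nominal date (22 or 28 months) satisfies a minimum worded as at least;
- what puts patients in order for the first 100;
- whether a patient with a recorded in-window failure who then leaves stays in the set.

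If these are settled only at analysis, membership could be decided with outcomes known, in a non-randomised trial that has one fixed cut-off.

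**Working it through.** **1. The plan's own error rates.** Inputs from Section 14.1.1: n = 100, claim if X ≤ 20, unacceptable rate 26%, acceptable rate 16%.

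- Exact type I error: P(X ≤ 20 | 0.26) = 0.1027. The plan states below 0.10.
- Exact type II error: P(X > 20 | 0.16) = 0.1121, so power is 0.888. The plan states below 0.15.

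The type II bound reproduces. The type I bound is narrowly missed by the exact test. It is met by a normal approximation without continuity correction: z = (20 − 26)/√(100 × 0.26 × 0.74) = −1.37, giving 0.086. That small gap belongs to the design at 26% and has nothing to do with the follow-up rule.

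**2. Statements on Group 2 timing, side by side.**

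| Place | Group 2 time after IMRT |
|---|---|
| 14.1.1, endpoint, historical rate, decision rule | 30 months |
| 14.1.1, follow-up aim | at least 30 months |
| 1.0, end of study period and total follow-up | 30 ± 2 months |
| 10.2, schedule table, 12.0, last evaluation | 30 ± 2 months |
| 14.1.1, entry to the primary set | at least 36 months |

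No other place gives 36 months as a time point.

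**3. Who could reach 36 months.**

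- Visits timed from IMRT end at 28 to 32 months, which is 4 to 8 months short.
- Surgeon visits timed from exchange: earliest 4 + 28 = 32 months, latest 8 + 32 = 40 months.
- Share needed: 2/3 of 120 to 130 irradiated patients is about 80 to 87 in Group 2. The lower figure applies if the 10 unirradiated Group 2B patients count towards the 130. Then 66/80 = 83% and 66/87 = 76% would have to reach 36 months.

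The documents do not say how many surgeon visits will be timed from exchange, so the share that would qualify cannot be computed from them.

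**4. Effect of changing 36 to 30.** n and the cut-off stay the same, so type I error 0.103 and power 0.888 (no loss) are unchanged.

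**5. Early leavers.** Let p be the true failure rate, and let f and m be the shares of failures and non-failures excluded and replaced. The observed rate is p(1 − f) / [p(1 − f) + (1 − p)(1 − m)]. The values of f and m are assumptions; the documents give none.

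| f, m | Observed rate at p = 0.26 | Type I error | Power at p = 0.16 |
|---|---|---|---|
| 10%, 10% | 0.260 | 0.103 | 0.888 |
| 10%, 0% | 0.240 | 0.207 | 0.947 |
| 20%, 30% | 0.287 | 0.033 | 0.758 |

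Equal loss returns the design values. Unequal loss moves the result either way.

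**6. Order of selection.** Suppose a recorded failure qualifies on its own date and a failure-free patient qualifies only at 24/30 months. If the first 34 and 66 are then taken by qualifying date, failures are over-represented even with no loss. In a simulation with 120 to 130 patients, 3.5 accrued per month (the middle of the plan's 3 to 4) and failures spread evenly over the window, a true 16% appears as about 18.7% to 19.7%. Power falls from 0.888 to about 0.68 to 0.59. Ordering by registration or IMRT start avoids this.

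**The case against.** The best defence is that any informed reader will take 36 as 30. The correct figure stands in the same paragraph, the failure-counting window is already fixed at 24/30 months, and the correction alters no design quantity. All of that stands. What remains is that the wrong figure is in the operative rule.

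A reader might infer that no Group 2 patient could ever qualify, or that a definite number would fall short. The documents do not support either. Footnote c permits later surgeon visits, and implant failure is a surgical event that can be ascertained at any time (Sections 11.1 and 12.0), so being followed need not mean having a scheduled visit. Nor can one say how many patients would be last seen before the nominal date because of the ± 2 month window: two clinicians see each patient and their visit timing is not given.

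A reader might also infer that the rule biases the failure rate downwards by dropping failures. That would need failures to leave more often than non-failures. The plan reports no loss rates and expects drop-off unrelated to toxicity. Section 13.0 (patients who quit are removed) and Section 9.2.1 (more than five consecutive missed treatments makes a patient inevaluable) bear on removal but do not settle how an earlier recorded failure counts. Section 14.1.3 does settle the parallel case for the PET scans, where a dropout is replaced unless the first scan already failed, so a comparable sentence for the primary endpoint is a reasonable request.

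**Conclusion.** The entry rule for the primary set is wrong as written for Group 2 and must be corrected. It contradicts the endpoint, the decision rule, the schedule and its own paragraph, and it means that the 66 Group 2 patients cannot be relied on. This rests on the text alone. Correcting it changes neither the test nor its error rates.

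The early-leaver question is a clarification. The type I errors of 0.033 to 0.207 shown above illustrate assumed loss patterns and do not estimate what will happen. The ordering question matters once recorded failures are kept in the set: selection by qualifying date could cost roughly 20 to 30 points of power under the stated simulation assumptions.

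**What to change.** In Section 14.1.1:

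- Change 24/36 to 24/30.
- State that a final visit inside the ± 2 month window meets the minimum, or that implant status at 24/30 months is confirmed from surgical records.
- Select the first 100 (at least 34 in Group 1 and 66 in Group 2) in order of registration or IMRT start, not by the date on which they qualify.
- State that a patient with an implant failure recorded within 24/30 months stays in the set whatever the later follow-up.
- Give one rule, applied in that same order, for patients whose status at 24/30 months stays unknown, with its error rates. As a guide, assume losses and failures are spread evenly in time. Replacing such patients gives type I error 0.084 and power 0.868 at 5% loss, and 0.038 and 0.777 at 20%. Counting them as failure-free gives 0.131 and 0.908 at 5%, and 0.250 and 0.954 at 20%.
- Keep n = 100, the cut-off of 20 and the binomial test.

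A cumulative-incidence estimate of implant failure at 24/30 months in all irradiated patients would be a useful supporting analysis but is optional.

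The cost is one corrected number, a few sentences and some record checking for patients who miss the final visit. No new visits are needed.
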